#### **4.7 Markers for Clinical Success**

Clinical success will be assessed using the Venous Clinical Severity Score (VCSS), which is measured at baseline and 6 weeks post-randomisation. The change in clinical classification in the Clinical, Etiologic, Anatomic, Pathophysiologic (CEAP) score at 6 weeks post-randomization from baseline will be reported and the chi-square test will be used to compare between the two arms. Similarly, change in VCSS score will be compared between the two arms using the t-test (assuming change in VCSS is normally distributed) or appropriate non-parametric test (if change in VCSS is not normally distributed).

Table 10 shows the proportions of patients with downgrade of clinical classification from C6 to C5 at 6-weeks post-randomisation and VCSS score. The VCSS scores at 6 weeks post-randomization and baseline will be summarised using boxplot for both arms (Figure 11).

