4.1 PATIENT RANDOMIZATION

The normal clinical team will make initial contact with potentially eligible patients at the referral visit.

Those who consent will be registered on the InForm ITM (Integrated Trial Management) System, a web-based data entry system, which is maintained by ICTU, and their eligibility for the study confirmed. A randomization list will be loaded onto the InForm system for each centre (as stratification will be by centre) before recruitment commences, having been prepared in advance by a statistician who is independent of the study. Each potential participant, if confirmed to be eligible, will be assigned the next available entry in the appropriate randomization list (i.e. without foreknowledge). Thereafter, treatment allocation will not be blinded (with the exception of assessment of ulcer healing – see 4.3.1). For patients with bilateral venous ulceration, the worst leg (according to the patient) will be designated the ‘reference leg’. Interventions may be performed on both legs, if deemed appropriate by the responsible clinician.

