4.3 STUDY OUTCOME MEASURES

4.3.1 Primary outcome measure

The primary outcome measure will be time to ulcer healing (from date of randomization to date of healing). For the purposes of this study, ulcer healing is defined as complete re-epithelialisation of all ulceration on the randomised (reference) leg in the absence of a scab (eschar) with no dressing required. Community or hospital healthcare staff, depending on the local model of care, will perform assessment of ulcer healing.

Data on the status of the reference leg will be collected throughout the study by research staff scrutinising community medical / nursing records and contacting the patient / community nursing teams by telephone (on a monthly basis at least).

If either the community nursing / medical staff or the patient believe that ulcer healing has been achieved, they will be asked to contact the local research centre immediately. This notification of possible ulcer healing will constitute a 'trigger' for research staff at the recruiting centre to arrange an urgent verification assessment by a member of the healthcare team (within 1 week).

Verification will be by clinical assessment and digital photography, to be repeated weekly for 4 weeks, unless otherwise agreed by the trial manager. The digital images will be evaluated by two blinded expert assessors in order to ascertain the date of healing, which will be considered the primary healing end-point. For the purposes of the trial healing will be defined as the complete re-epithelialisation of the ulcerated (reference) leg in the absence of a scab (eschar) with no dressing required. Healing cannot be assumed if a scab present.

Disagreements will be resolved through discussion with involvement of a third blinded expert reviewer if necessary. This approach will be applied to patients in both treatment arms and is consistent with the methods utilized in other large HTA funded leg ulcer trials (e.g. VenUS IV). Legs deemed to have an open ulcer on clinical assessment would continue within the study. If healing is confirmed by clinical and

blinded photograph assessments at the first verification visit, the date of healing notification (by patient or community nurse) will be taken as the date of ulcer healing.

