4. Health Economic Assessment: A within-RCT cost effectiveness analysis will be carried out based on the data collected in the trial. Resource use items in hospital and community care related to the treatment of venous ulceration or complications will be recorded for each patient at each follow-up. Resource use will be multiplied by UK unit costs obtained from published literature, HRG costs, and manufacturers' list prices to calculate overall costs. A standard tariff will be applied for each bandage change. Utilities (QALYs) will be calculated from the EQ-5D questionnaire administered to patients at baseline, 6 weeks, 6 months, 12 months and at one time point between October 2018 and March 2019. The extent of missing data will be assessed and appropriate methods to handle missing data will be applied if necessary. The incremental cost-effectiveness ratio will be calculated and compared to current UK decision making thresholds. Discounting will be applied at the standard rate. Sensitivity analysis will be carried out to test the robustness of results to alternative assumptions (for example, about missing data, or using per-protocol estimates of treatment effect) or alternative data (for example, about unit costs). Probabilistic sensitivity analysis will be carried out using bootstrapping. A decision model will also be constructed to take account of

outcomes (such as recurrence or healing) that might occur beyond time horizon of the RCT, or to take account of other relevant comparators in this patient group.

5. Other Markers of Clinical Success: The Venous Clinical Severity Score (VCSS) will be assessed at 6 weeks. In addition, the incidence of complications related to the endovenous intervention as well as the presence of residual / recurrent varicose veins will also be assessed at 6 weeks in the early arm.

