#### **4.9 Derived Variables**

1. Deep vein reflux is defined as iliac, femoral, popliteal or crural deep vein reflux detected by Duplex scan.
2. Deep vein obstruction is defined as iliac, femoral, popliteal or crural deep vein outflow obstruction detected by Duplex scan.
3. Time to ulcer healing will be calculated as the difference between the final healing date and date of randomisation. Final healing date is collected in the InForm database and this variable is entered by trial manager after experts agree on the healing date. Patients will be censored at the time of last follow-up if they are dead, withdrawn or lost to follow-up before primary ulcer healing. The follow-up time is one year after randomisation and thus patients with unhealed primary ulcer at one year after randomisation will be also censored.
4. One-year ulcer free time will be calculated as total follow-up time in days (i.e. one year or time to the last follow-up if patients are dead, withdrawn or lost to follow before one year) deducting the total duration of ulcers, including primary ulcer and recurrences.
5. Ulcer chronicity will be calculated as the difference between the date of current ulcer appeared and the date of randomisation.

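### The SAP tests the 6-week C6-to-C5 downgrade between arms without tying it to the blinded healing adjudication, although this is in effect ulcer healing by 6 weeks and an expert-agreed healing date is already held

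*SAP*

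**What the plan says.** SAP 4.7 reports the change in CEAP clinical class from baseline to 6 weeks and states that "the chi-square test will be used to compare between the two arms". It assigns to Table 10 the "proportions of patients with downgrade of clinical classification from C6 to C5 at 6-weeks post-randomisation". It names no assessor, no source for the grade and no link to the healing adjudication. SAP 2.5 tests secondary outcomes at a two-sided 5% level without adjustment for multiplicity.

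The protocol does not schedule CEAP at 6 weeks. Section 6.3 lists it at baseline. Section 4.3.2, item 5, says that "The Venous Clinical Severity Score (VCSS) will be assessed at 6 weeks" and adds complications and residual or recurrent veins, but not CEAP. Section 6.4.1 gives the 6-week visit a clinical assessment, a wound tracing and photograph and, in the early arm, a duplex scan.

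On blinding, protocol 4.1 (repeated in SAP 1.6) says that "treatment allocation will not be blinded (with the exception of assessment of ulcer healing". Protocol 4.3.1 describes the blinded part: "The digital images will be evaluated by two blinded expert assessors in order to ascertain the date of healing". The result is stored: SAP 4.9 says that "Final healing date is collected in the InForm database", entered once the experts agree.

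**The concern.** Inclusion requires a current leg ulcer (protocol 3.2). On the usual meaning of the classes, a patient who moves from C6 to C5 by 6 weeks has healed. That is the primary event read at an early time point, but the SAP does not send it through the process that protects the primary endpoint. A leg could therefore count as healed in Table 10 and unhealed in the primary analysis.

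If clinic staff who know the allocation do the grading, a modest tendency to call ulcers healed after ablation could make a marker of clinical success nominally significant. A reader of the report could then take it as separate support for the primary result, when it is the same event measured with less protection.

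**Working it through.** **1. The plan's own figure.** Protocol 7.1 gives 60% v 75% healed at 24 weeks, 90% power, 10% dropout, 254 healed ulcers, 416 subjects (208 per arm) and a target of 450 (225 per arm).
- HR = ln(0.25)/ln(0.40) = 1.513.
- Freedman events = (1.960 + 1.282)² × [(1.513 + 1)/(1.513 − 1)]² ≈ 253, against 254 stated.
- Mean healing proportion 0.675: 253/0.675 ≈ 375, and 375/0.90 ≈ 417, against 416 stated.

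The sample size reproduces and does not depend on the CEAP item. The documents give no rate or power for the downgrade.

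**2. Expected healing by 6 weeks.** Assuming constant hazards through the 24-week rates:
- Standard: 1 − 0.40^(6/24) = 20.5%.
- Early: 1 − 0.25^(6/24) = 29.3%, a difference of 8.8 points.

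**3. What one-sided over-calling would do with no true effect.** Let p₁ be the proportion graded healed in the standard arm, p₂ that in the early arm, n the number per arm, d = p₂ − p₁ and p̄ = (p₁ + p₂)/2. Then

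se₀ = √[2p̄(1 − p̄)/n], se₁ = √{[p₁(1 − p₁) + p₂(1 − p₂)]/n},

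P(reject) = 1 − Φ[(1.96 se₀ − d)/se₁] + Φ[(−1.96 se₀ − d)/se₁].

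With p₁ = 0.205 and n = 225:
- 3 points (p₂ = 0.235): se₀ = 0.0391, se₁ = 0.0390; P ≈ 12%.
- 5 points (p₂ = 0.255): se₀ = 0.0397, se₁ = 0.0396; P ≈ 24%.

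Expressed instead as the share of still-open early-arm ulcers graded C5, so that p₂ = 0.205 + 0.795 × share:

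| Share mis-graded | p₂ | P(reject), 208 to 225 per arm |
|---|---|---|
| 0% | 20.5% | 5% |
| 2% | 22.1% | 7% |
| 5% | 24.4% | 16–17% |
| 10% | 28.4% | 47–50% |

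If the true 6-week rate lies between 15% and 29%, a 5% share gives 12–22%. Equal over-calling in both arms makes d = 0 and leaves the rate near 5%. The over-calling sizes are assumptions; nothing in the documents supports a particular value.

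**4. The adjudicated measure.** At the rates in step 2, a two-proportion comparison of healing by 6 weeks has about 55% power with 208 per arm and 58% with 225, with no new data. SAP 4.5 already takes the 24-week rate from the Kaplan-Meier analysis, and Table 7 has a 12-week row.

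**The case against.** The strongest reply is that the documents are silent rather than wrong. A reader might infer that they prescribe unblinded clinic grading of CEAP at 6 weeks. They do not: no assessor is named, and a wound photograph is taken at that visit. Open-label grading is an inference from open allocation and the absence of any stated blinding. That stands as a limit on the wording, but silence about the assessor of a tested outcome still needs repair.

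A reader might also infer that the grade uses a looser definition of healing. The documents do not support this either. Both define healing for the study, and SAP 4.7 sets no other standard. What is missing is a stated link to that definition and to the photograph reading.

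A third tempting reading sets a fully blinded endpoint against an unblinded marker. Protocol 4.3.1 says "Community or hospital healthcare staff, depending on the local model of care, will perform assessment of ulcer healing", so notification and clinical verification are open, and a notification date confirmed at the first verification visit becomes the healing date. The photograph readers guard against false calls of healing, not against differential timing of notification. The replacement is therefore only partly blinded. It remains better protected than a grade with no planned photograph check.

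Finally, the replacement is a point on the healing curve already planned, so it adds little information. That is a fair cost. Its answer is to label the item for what it is.

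**Conclusion.** The point holds as a low-severity correction. SAP 4.7 tests a 6-week outcome that the protocol does not schedule, that in effect repeats the primary event, and that no text ties to the blinded adjudication. This rests on two inferences: the usual meaning of C5 and C6, and open-label grading. SAP Table 4 carries a baseline C5 row, but the inclusion criteria suggest that few if any patients would fall there.

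The 12% and 24% rejection rates show how sensitive the test would be to assumed over-calling in one arm. They do not estimate bias in this trial. A reader might infer that the primary result is compromised. It is not: time to healing uses the adjudicated date (SAP 4.9), the 24-week rate comes from the Kaplan-Meier analysis (SAP 4.5), and the sample size is untouched.

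**What to change.** In SAP 4.7 and Table 10:

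1. Take the between-arm comparison of 6-week healing from the adjudicated healing date, as the Kaplan-Meier estimate at 6 weeks with its confidence interval. Patients who die or withdraw unhealed before then are censored, as SAP 2.6 and 4.9 already provide. A plain healed or not-healed coding would count them as unhealed.
2. Label it 'healed by 6 weeks', and state that it belongs to the primary healing data and is not independent evidence.
3. Report any clinic CEAP grade descriptively, marked open-label, without a test.
4. Keep VCSS as planned, labelled as an unblinded assessment.

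The cost is SAP wording only, because the date is already in InForm and the sample size does not change. There are three downsides. The item becomes a point on the planned curve. It measures whether the ulcer ever healed by 6 weeks and not its status at the visit, so an ulcer that healed and recurred before the visit counts as healed. It also stays only partly blinded, because healing notification is open.

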#### **4.8 Safety Data**

The safety data, including adverse events (AEs) and serious adverse events (SAEs) will be provided in a tabular format for the two arms (Table 11 and Table 12). AEs will be summarised by description and outcome and SAEs will be summarised by SAE reason, frequency, severity, and relationship to treatment, outcome and expectedness.

#### **4.9 Derived Variables**

1. Deep vein reflux is defined as iliac, femoral, popliteal or crural deep vein reflux detected by Duplex scan.
2. Deep vein obstruction is defined as iliac, femoral, popliteal or crural deep vein outflow obstruction detected by Duplex scan.
3. Time to ulcer healing will be calculated as the difference between the final healing date and date of randomisation. Final healing date is collected in the InForm database and this variable is entered by trial manager after experts agree on the healing date. Patients will be censored at the time of last follow-up if they are dead, withdrawn or lost to follow-up before primary ulcer healing. The follow-up time is one year after randomisation and thus patients with unhealed primary ulcer at one year after randomisation will be also censored.
4. One-year ulcer free time will be calculated as total follow-up time in days (i.e. one year or time to the last follow-up if patients are dead, withdrawn or lost to follow before one year) deducting the total duration of ulcers, including primary ulcer and recurrences.
5. Ulcer chronicity will be calculated as the difference between the date of current ulcer appeared and the date of randomisation.

## 5. Sensitivity analysis

As a sensitivity analysis, we will perform a per-protocol analysis by excluding patients with protocol violations. This sensitivity analysis will cover all primary and secondary outcomes. As the per-protocol analysis leads to the optimal effect of EVRA and could bring attrition bias, we will interpret the results of pre-protocol analysis with extreme caution. The surgeon data is collected separately and not included in the InForm database. If the surgeon data can be merged into the main database and, we will carry out another sensitivity analysis by including surgeon as a random effect in the Cox regression analysis for primary outcome.

## Tables

Table 1 Baseline characteristics between the EVRA and standard treatment group\*

	EVRA	Standard
	N=	N=
Age		
Height		
Weight		
BMI		
Gender		
Male		
Female		
Smoking		
Never		
Former		
Current		
Ethnicity		
White		
Mixed		
Asian		
Black		
Chinese		
Other		
EQ-5D		
Mobility		
Self-care		
Usual activities		
Pain/discomfort		
Anxiety/depression		
Health state score		
SF-36		
Physical function		
Role-Physical		
Body pain		
General Health		
Vitality		
Social Functioning		
Role-Emotional		
Mental Health		
Total AVVQ		

\* Data presented as frequency (percentage) for categorical variables and mean (SD) for continuous variables

Table 2 Summary of medical history & concurrent medication\*

	EVRA N=	Standard N=
Previous pregnancy†		
Yes		
History of DVT in pregnancy (yes)		
No		
Hormone therapy†		
None		
Previous HRT		
Current HRT		
Previous OC		
Current OC		
Previous Rheumatoid disease (yes)		
Previous DVT		
Current antiplatelet therapy		
None		
Aspirin		
Clopidogrel		
Other		
Current anticoagulation therapy		
None		
Warfarin		
New oral anticoagulants		
Other		
Current Steroids		
Yes		
No		
Current Trental (pentoxifylline)		
Yes		
No		
Diabetes		
Yes		
No		

\* Data presented as frequency (percentage) for categorical variables

† Female only

Table 3 Summary of ulcer history\*

	EVRA	Standard
	N=	N=
Previous ulcer (yes)		
Ulcer dressing		
NA		
Inadine		
Other		
Baseline Compression		
None		
KTwo		
Three-layer bandage		
Four-layer bandage		
European short stretch		
Stocking		
Other		
Time of wearing		
Day & night		
Day only		

\* Data presented as frequency (percentage) for categorical variables

Table 4 Characteristics of current ulcer\*

	EVRA N=	Standard N=
Time since ulcer diagnosis (months)		
Trial ulcer leg		
Right		
Left		
Ulcer location		
Lateral		
Medial		
Circumferential		
Ulcer size (cm^2)		
Duplex Scan: Deep Vein		
Normal		
Abnormal †		
Reflux		
Outflow obstruction		
CEAP Score		
Clinical signs – grade		
C 5		
C 6		
Clinical signs – presentation		
Asymptomatic		
Symptomatic		
Etiologic classification		
Primary		
Secondary		
Deep		
No venous cause		
Anatomic distribution		
Superficial		
Perforator		
Deep		
Pathophysiologic dysfunction		
Reflux		
Obstruction		
Both		
No venous cause		
VCSS Score		
Palpable pedal pulses		
Yes		
No		

\* Data presented as frequency (percentage) for categorical variables and median (range) for continuous variables

†A patient can have both deep vein reflux and obstruction

Table 5 Treatment summary

	EVRA N=	Standard N=
Endothermal only		
Foam only		
Mechanochemical ablation (MOCA) only		
Endothermal and Foam		
MOCA and Foam		

\* *Data presented as frequency (percentage)*

Table 6 Time to ulcer healing in patients with chronic venous ulceration (Cox regression model)

	Univariate model*		Multivariate model†	
	HR (95% CI)	P value	HR (95% CI)	P value
Treatment				
Standard arm				
EVRA				
Age (yrs)				
Ulcer chronicity (mths)				
Ulcer size				
1 st Quartile				
2 nd Quartile				
3 rd Quartile				
4 th Quartile				

\* Adjusted by centre (centre included in the model as a random effect)

† Adjusted by centre, age, ulcer size and chronicity (centre included in the model as random effect and age, ulcer size and chronicity as fixed effects).

Table 7 Summary of 12-week and 24-week ulcer healing rate and ulcer free time\*

	EVRA N=	Standard N=
12-week ulcer healing rate		
24-week ulcer healing rate		
No. of patients with recurrent ulcer		
Ulcer free time		

\* Data presented as frequency (percentage) for categorical variables and median (range) for continuous variables

Table 8 Multiple linear regression (ordinal regression) for ulcer free time (days) to 1 year in patients with chronic venous ulceration

	Univariate model*		Multivariate model†	
	Coefficient (95% CI)	P value	Coefficient (95% CI)	P value
Treatment				
Standard arm				
EVRA				
Age (yrs)				
Ulcer chronicity (mths)				
Ulcer size				
1 st Quartile				
2 nd Quartile				
3 rd Quartile				
4 th Quartile				

\* Adjusted by centre (centre included in the model as a random effect)

† Adjusted by centre, age, ulcer size and chronicity (centre included in the model as random effect and age, ulcer size and chronicity as fixed effects).

Table 9 Summary of quality of life (AVVQ, EQ-5D, SF36) at baseline, 6 weeks, 6 months and 12 months after randomisation

	N	EVRA	Standard
		Mean (SD)	Mean (SD)
AVVQ			
Baseline			
6 weeks			
6 months			
12 months			
EQ-5D health score			
Baseline			
6 weeks			
6 months			
12 months			
EQ-5D index value			
Baseline			
6 weeks			
6 months			
12 months			
SF-36 physical health			
Baseline			
6 weeks			
6 months			
12 months			
SF-36 mental health			
Baseline			
6 weeks			
6 months			
12 months			

\* Data presented as mean (SD) or median (IQR), as appropriate

Table 10 Summary of clinical success at 6 weeks after randomisation

	EVRA	Standard
	N=	N=
VCSS total score		
Yes		
No		

\* Data presented as frequency (percentage) for categorical variables

Table 11 Summary of adverse events

	EVRA	Standard
	N=	N=
No. surgical procedures		
Total number of AEs		
Description of AE		
Systemic		
Local		
Outcome		
Recovered		
Not yet recovered		
Death		
Unknown		
Missing		

\* Data presented as frequency (percentage) for categorical variables

Table 12 Summary of serious adverse events

	EVRA N=	Standard N=
No. surgical procedures		
Total number of SAEs		
Serious reason		
Death		
Life threatening		
Persistently disabling		
Hospitalisation required		
Congenital abnormality		
Other		
Frequency		
Single Episode		
Intermittent		
Frequent		
Continuous		
Unknown		
Severity		
Mild		
Moderate		
Severe		
Life threatening or disabling		
Relation to procedure		
Not related		
Unlikely		
Possible		
Probable		
Definite		
Outcome		
Recovered		
Not yet recovered		
Death		
Unknown		
Expectedness		
Expected		
Unexpected		

\* Data presented as frequency (percentage) for categorical variables

## Figures

**Figure 2 CONSORT diagram of the study population**

**Figure 3 Kaplan-Meier curve showing ulcer healing time in the EVRA and standard (delayed) arm**

**Figure 4 Forest plot showing the treatment effect on time to healing by pre-defined sub-groups**

**Figure 5 Forest plot showing the treatment effect on time to healing by different treatments**

**Figure 6 Forest plot showing the treatment effect on ulcer free time by pre-defined sub-groups**

**Figure 7 Forest plot showing the treatment effect on ulcer free time by different treatments**

**Figure 8 Time trend of EQ5D: a) Health Score; b) Index Value in the two arms**

**Figure 9 Time trend of SF-36 in the two arms**

